Phase 2 Study: Intranasal Oxytocin for Treatment of Infants and Children with Prader-Willi Syndrome in Nutritional Phase 1a

NCT03245762

8/17/2017

**Phase 2 Study: Intranasal Oxytocin for Treatment of Infants and Children with Prader-Willi Syndrome in
Nutritional Phase 1a**
[name], Principal Investigator

BACKGROUND AND SIGNIFICANCE

Prader-Willi syndrome (PWS) is a rare, complex multisystem genetic disorder arising from the lack of expression of paternally inherited imprinted genes in the 15q11-q13 chromosomal region. The syndrome includes severe neonatal hypotonia with decreased appetite and impaired suck necessitating assisted feeding (nutritional phase 1a), followed by a period of improved appetite (nutritional phase 1b) (Miller et al, 2011). Weight gain without a change in appetite begins around age two years (nutritional phase 2a). Then an increased interest and awareness of food, with increased anxiety and behavioral problems typically begins around age 4-5 years (nutritional phase 2b) (Goldstone et al, 2012; Miller et al, 2011). This is followed by an insatiable appetite with worsening behavioural manifestations beginning around age 8 (nutritional phase 3) (Goldstone et al, 2012; Miller et al, 2011). These appetite issues are combined with other endocrine problems probably due to hypothalamic dysfunction. The pathophysiological mechanism of the occurrence of the various nutritional phases of PWS is unknown.

Nutritional phase 1a is characterized by the need for assisted feeding. The feeding can typically be accomplished using a special nipple/bottle, placement of a nasogastric tube, or placement of a gastrostomy tube. However, this is a dangerous time for infants with PWS, and has a high rate of morbidity and mortality due to aspiration and respiratory failure (Nagai et al, 2005). In addition to these intrinsic risks associated with the poor suck and swallow in infants with PWS, the delay in development of normal feeding patterns may be the cause of the nearly universal expressive speech delay seen in individuals with PWS (Miller and Plager, 2014). Normal sucking and swallowing, reflect the early developmental pathways that are the basis for later emergence of successful communication skills, so potentially correcting the sucking and swallowing abnormalities in infancy could change speech and language issues in the future. Feeding and swallowing skill development parallels psychosocial milestones of homeostasis, attachment, and separation/individuation. Mothers of infants with PWS often describe a feeling of lack of attachment or lack of bonding with their child due to the lack of suckling and responsiveness of the children.

Oxytocin nasal spray enhances face processing emotion recognition. There is growing evidence that oxytocin abnormalities may underlie repetitive stereotypic behaviors and that administering oxytocin may reduce restrictive repetitive behaviors. As they grow up, individuals with PWS have a clinical phenotype similar to autism. They exhibit disruptions in social engagement, including impairment in communication skills, restricted, repetitive and stereotyped patterns of behavior, and decreased ability for social recognition. Social recognition requires a complex set of processes: social approach and investigation, sensory processing and learning and memory. Oxytocin plays a very important role in social recognition, maternal behavior and maternal–infant bonding (Pedersen & Prange 1979; Kendrick *et al.* 1997; Ferguson *et al.* 2001).

Oxytocin is produced in the hypothalamus, including the supraoptic and paraventricular nucleus (Gainer, 1998). Magnocellular neurons in these nuclei send projections to the posterior pituitary, where oxytocin is released into the bloodstream and has effects on parturition and milk ejection during lactation. Swaab and colleagues (1995) reported a deficit in the oxytocin (OT)-producing neurons of the paraventricular nucleus (PVN) in the brain of these patients and Bittel and colleagues (2007) reported decreased oxytocin receptor gene function in PWS. In addition to decreasing appetite, OT is involved in establishing and maintaining social standards. Indeed, it has recently been shown in a double blind placebo study, that OT administration to adults with PWS significantly decreased depressive mood tendencies and tantrums while increasing trust in others, with data supporting a trend to decrease appetite with higher satiety (Tauber et al., 2011). Moreover, in a PWS

knock-out mouse model for the *Mage12* gene, a single OT injection at 5 hours of life prevented early death observed in 50% of new-born mice by recovering a normal suck (Schaller et al, 2010).

Proposed Mechanism of Oxytocin in Prader-Willi Syndrome – Neonatal Period:

Pathophysiology: Dysfunction of the oxytocin (OT) system has been implicated in the pathophysiology of PWS. Oxytocin (OT) is a nonapeptide synthesized in the paraventricular (PVN) and supraoptic nuclei (SON) of the hypothalamus. It has been proposed to play a role in social recognition, pair bonding, anxiety, maternal behaviors, metabolism, food motivation and hyperphagia. OT receptors are expressed in numerous brain regions including the amygdala, ventromedial hypothalamus, and the brainstem. The number and size of OT neurons in the PVN is significantly reduced in PWS (Swaab et al, 1995; Bittel et al, 2007). Although many investigators have attributed the poor suckling and failure to thrive in infants with PWS to their hypotonia, the poor feeding is accompanied by a lack of interest and/or avoidance of food. The great majority of infants with PWS will not wake to feed, will not open their mouth to accept the bottle, and do not cry for food.

Animal Models:

In animal models, oxytocin has been shown to play a critical role in social processing, recognition, and bonding, and also to influence stereotyped behaviors such as exaggerated grooming. In mammals, OTRs are expressed at higher levels in early development. OT knockout mice have been shown to maintain olfaction and cognitive performance, but suffer deficits in social recognition that were recovered by intraventricular OT but not by AVP administration. Compared to wild type, OTR knockout mice emit fewer ultrasonic vocalizations in response to social isolation, experience deficits in social discrimination, and demonstrate more aggressive behavior.

Human Data:

Synthetic OT (Pitocin/Syntocinon) is a 9 residue cyclic peptide; the hormone is prepared synthetically to avoid possible contamination with vasopressin and other small polypeptides with biologic activity. There have been multiple studies of IN-OT in lactating and non-lactating women which provide data regarding the safety of both the peptide and administration route. These studies have systematically reported none or only minimal side effects. In addition, there have now been at least a dozen published studies using IN-OT in healthy adults; here too, minimal side effects have been reported. Finally, data from a 6 week pilot treatment study in children with autism indicate that the medication was very well tolerated compared to placebo. Side effects of IN-OT may include nasal irritation, runny nose, or tearing of the eyes, shortness of breath, closing of the throat; hives; swelling of the lips, face, or tongue; rash; or fainting. Additional rare side effects reported in single cases and of unknown relationship with the medication include unusual bleeding, convulsions, nausea, drowsiness, headache, anxiety, and sad mood. Uterine contractions may occur in women and are more likely to occur in pregnant women especially at the end of pregnancy. Estrogen mediates Pitocin’s effect on uterine muscle. Large doses of **intravenous** OT decrease both systolic and diastolic blood pressure through a transient relaxation of vascular smooth muscle. Any OT-induced decrease in blood pressure is followed by a mild but sustained increase. IN-OT, which will be used in the present study, **has not been found to substantially affect blood pressure**. Because few studies have reported on the use of IN-OT, there is a strong need for the collection of such side-effect data, as proposed in this project (Figure 1).

[figure not shown]

Figure 1: Oxytocin physiologic effects

Rationale for Intranasal Administration

OT is metabolized by chymotrypsin in the GI tract and therefore is not administered orally. Currently, the only form of OT that is available in Canada and the US is the intravenous form and although this formulation has been found to produce behavioral effects, it is invasive to administer and the extent to which this formulation crosses the blood-brain barrier is not known. However, a recent study by Ring and colleagues 2006, speaks to the issue of brain penetration. This study investigated the anxiolytic effects of centrally and peripherally administered OT in male mice. Although substantially larger doses of OT were required for peripheral administration to achieve comparable behavioral effects to those achieved by central administration (suggesting that OT exerts its anxiolytic effects through its action on the CNS), nonetheless, peripheral administration produced behavioral effects. These researchers argue, that “the anxiolytic-like effects of peripherally administered OT can be accounted for by the passage of relatively small, but sufficient, amounts of the peptide across the blood brain barrier (BBB) into the CNS” (Ring et al, 2006). The claim that peripherally administered OT penetrates the brain and exerts its behavioral effects by acting on the CNS was further supported by the finding in this study that a centrally administered OT antagonist that does not cross the BBB was able to fully reverse the anxiolytic-like effects of peripherally administered OT. Intravenous OT, however, is not practical for treatment studies.

One alternative is IN-OT; this form of administration is absorbed through the highly permeable nasal mucosa and has been shown to pass the BBB; it is also easy to self-administer. Withdrawal from the US and Canadian market by the manufacturer of the IN-OT (syntocinon Novartis) in 1997 and 1992 respectively, was not related to any safety issues but was at the request of the manufacturer, for poor market profits. Intranasal oxytocin has previously been approved for marketing in the United States from March 20, 1962 until its withdrawal from the market on August 7, 1997. At the time of its withdrawal from the market, the indication for IN-OT was for induction of labor in adults. The Federal Register notice issued on that date [Federal Register, Vol. 62, No. 152, Docket No. 97N-0326, pp. 42575 –42577], clearly states that this withdrawal was at the request of the manufacturer, because the drug was no longer being marketed. No safety reasons were cited in connection with the withdrawal. The intranasal form of OT remains on the market outside the US and Canada (e.g. Switzerland) and pitocin administered via intravenous infusion is still available in the US and Canada. The use of IN-OT in infants and young children is not anticipated to increase the risk over what is known for older children and adults.

Objective: The overall objective of this Phase 2 trial is to compare the change from baseline to day 5 of IN-OT on suck and swallow competency in infants/children with PWS who are in nutritional phase 1a. (The follow-up swallow study will occur the day after treatment visit day 5.) We have obtained an IND for the use of IN-OT for PWS (IND 120852) and will utilize IN-OT and matching placebo (Manufactured by Novartis as Syntocinon).

Study Hypothesis 1: We hypothesize that replacing OT in infants and children who are in nutritional phase 1a will improve their suck and swallow, potentially even eliminating the need for gastrostomy tubes and nasogastric tubes for feeding, and decreasing the risk of aspiration with oral feeding.

Study Hypothesis 2: We hypothesize that replacing OT in infants and children with PWS will result in improved eye contact, daytime alertness, and feelings of bonding between the parents and the infant.

We will evaluate the effects of IN-OT compared to placebo on suck and swallow competency of infants with PWS using videofluoroscopic swallow study. Competency of suck/swallow will be determined by a board-certified speech and language pathologist who will be blinded to the treatment arm of each patient. Additionally, penetration and aspiration risk will be assessed during the videofluoroscopic study to assess safety of oral feeding. Additionally, we will have the speech pathologist evaluate each infant and complete an Early-Feeding Skills Assessment (EFS) form prior to the first swallow study evaluation and on Day 5, one day before the final swallow study (Appendix 1).

Standard of care recommendation for infants with PWS is a videofluoroscopy swallow study prior to being discharged home on any oral feeding. This test is often repeated clinically up to 5 times per patient, depending on their degree of swallowing dysfunction. Therefore, this study will not be adding significant radiation risk beyond what is typically performed clinically.

The Mother-Infant Bonding Questionnaire (MIBQ) has been widely used to assess maternal emotional involvement with infants, and has been validated in the postpartum period (Klier, 2006; Ohara et al, 2016). This questionnaire will be administered before the first medication/placebo administration and at the completion of Day 5 of the study (Appendix 2).

The Tobii Eye Tracking system has been used extensively and validated in evaluating infant gaze (Jakobsen et al, 2016; Smith et al, 2013). Standardized assessments are available using this system with recording done during the assessment using a digital video camera. Areas of interest are defined around the eye and mouth region and infants are shown pictures of female faces displaying four different dynamic sequences, each lasting approximately 16 seconds (Figure 3).

Figure 3: Face presentation during eye tracking experiment

Dosing and Administration: The dose of OT to be used in this study was determined based on data from IN-OT trials in infants with PWS in Toulouse, France (Tauber et al, submitted). Doses administered in that study were: 4 IU/day of IN-OT; 4 IU twice a day; or 4 IU every other day.

- Administration of first dose of 4 IU IN-OT or placebo

OT or placebo will be given by the PI, who has been trained in the method of administration of using a rhinal tube to administer the nasal spray, and who will give the drug or placebo to every patient enrolled in the study. The spray will be given as 1 dose (4 IU) measured squirt into one nostril (nostril will alternate daily) via rhinal tube device. Vital signs will be taken immediately after the administration is complete, and every 15 minutes times four.

Day 2

Subjects will present to the clinic/CRC for day 2 study procedures. During this visit the following will occur:

- Focused physical exam by PI
- Vital signs (T,P,BP,R) - pre and immediately post OT administration, then every 15 minutes X4
- Weight
- Blood draw for safety labs (glucose, potassium, sodium), prior to OT administration
- IN-OT or placebo administration

Day 3

Subjects will present to the clinic/CRC for day 3 study procedures. During this visit the following will occur:

- Focused physical exam by PI
- Vital signs (T,P,BP,R) - pre and immediately post OT administration, then every 15 minutes X4
- Weight
- Adverse event evaluation
- OT administration (see visit 1 for detailed instructions)

Day 4

Subjects will present to the clinic/CRC for day 4 study procedures. During this visit the following will occur:

- Focused physical exam by PI
- Vital signs (T,P,BP,R) - pre and immediately post OT administration, then every 15 minutes X4
- Weight
- Adverse event evaluation
- OT administration (see visit 1 for detailed instructions)

Day 5

Subjects will present to the clinic/CRC for day 5 study procedures. During this visit the following will occur:

- Focused physical exam by PI
- Vital signs (T,P,BP,R) - pre and immediately post OT administration, then every 15 minutes X4
- Weight
- Adverse event evaluation
- OT administration (see visit 1 for detailed instructions)
- Blood draw for safety labs (glucose, potassium, sodium), prior to OT administration
- Blood draw for study labs (OT, ghrelin, insulin, cortisol, orexin A), prior to OT administration
- Early-Feeding Skills Assessment (EFS) by speech pathologist
- Completion of MIBQ by parent

Day 6 – Videofluoroscopy swallow study; Eye Tracking measurement

Study Intervention: OT and placebo will be administered intranasally. There have been several trials of IN-OT in children, adolescents, and adults with PWS, and one successful trial of IN-OT in infants with PWS. To date, no trials of IN-OT in individuals with PWS have recorded any serious adverse effects and the treatment has been well tolerated.

Follow-Up: Parents will be contacted by phone one week and one month after their child receives his/her last dose of study medication/placebo. During this phone call parents will be asked about any side effects or concerns regarding the study treatment and/or study procedures. Parents will be reminded to contact the PI or Sub-I with any questions or concerns regarding the study.

Recruitment of Participants: Participants will be recruited from the clinic patients of the PI.

Outcome Measures: Project outcomes will be determined by changes in eye tracking and in aspiration and penetration on videofluoroscopy swallow study from baseline to the day following Day 5 (i.e., Day 6), and comparisons of Day 6 measures between active treatment and placebo groups.

Data and Safety Monitoring Plan

The study protocol will be reviewed and approved by the Food and Drug Administration (FDA) before submission to the UF-IRB for approval. Participant enrollment may only begin with IRB approved consent forms.

This is an interventional pilot study that meets the federal definition of moderate risk.

Safety measures in place to mitigate risk

The primary safety measures in place to mitigate risks are close monitoring of the participants during the study, 24 hour availability by pager for caregiver clinic concerns, abilities to schedule additional appointments whenever clinically required and close monitoring of laboratory parameters. If a subject requires emergency care, they will be advised to call 911 and preferable be taken to the nearest emergency room. They should also call the 24 hour beeper so that the investigator on call may contact the emergency room.

All risks will be reviewed in the consent form, and families will be informed of their right to refuse any procedure or withdraw from the study at any time. Trained and experienced staff will conduct all medical assessments. Individuals who are experiencing any worsening of symptoms identified by PI or speech pathologist will be discontinued from the trial and provided with appropriate referrals for follow-up care.

Lastly, the patients will be contacted by telephone one week and one month after study termination for each subject to assure that discontinuation of the medication has not caused any side effects or distress. The

subjects will be advised to call the PI or the 24 hour beeper for any concerns for the month past termination, and will always be able to set an appointment in addition to study visits, to address concerns regarding safety.

Study Oversight

The PI has primary oversight responsibility of this clinical trial. The PI will assemble a Data (Observational) Safety Monitoring Board (D/OSMB) which will have oversight responsibility of the Data Safety Monitoring Plan (DSMP) for this clinical trial. The D/OSMB will review accrual, patterns and frequencies of all adverse events, and protocol compliance every 6 months. The D/OSMB will make recommendations regarding the continuation status of the protocol.

The Principal Investigator and research team (co-Investigator, research nurses, clinical trial coordinator, and data manager) are responsible for identifying adverse events. Aggregate report- detailed by severity, attribution (expected or unexpected), and relationship to the study drug/study procedures – will be available from the DMCC for site review. Adverse events will be reviewed monthly by the research team. The research team will then evaluate whether the protocol or informed consent document requires revision based on the reports.

Definitions and Standards

The FDA defines an adverse event as: "...an unfavorable and unintended sign, symptom or disease associated with a participant's participation in a medication trial."

Serious adverse events include those events that: "result in death; are life-threatening; require inpatient hospitalization or prolongation of existing hospitalization; create persistent or significant disability/incapacity, or a congenital anomaly/birth defects."

An unexpected adverse event is defined as any adverse experience...the specificity or severity of which is not consistent with the risks of information described in the protocol.

Expected adverse events are those that are identified in the research protocol as having been previously associated with or having the potential to arise as a consequence of participation in the study

All reported adverse events will be classified using the current version of the Common Terminology Criteria for Adverse Events (CTCAE) developed and maintained by CTEP at National Cancer Institute.

Adverse Events and Risks:

Intervention

The most recent monograph for the intranasal form of the oxytocin medication only lists allergic rhinitis, and uterine contractions as side effects. Below we have listed other known side effects of oxytocin. Because very few studies have reported on the extended use of intranasal OT, there may be other unknown side effects. The PI (or a covering clinician) will be available at all times to study participants in the event of a clinical emergency; both this availability and how to reach the investigators in an emergency will be clearly communicated orally and in writing to study participants. All study interventions will be provided free of cost.

The following side effects are fairly common with intranasal oxytocin treatment and are usually mild:

- Dry or runny nose
- Headache
- Nausea
- Nasal irritation
- Tearing of eyes

Side effects that are less common, but may require medical attention include:

- Unusual bleeding (vaginal)
- Excessive drowsiness
- Lack of appetite

Side effects that are rare but serious include

- Alterations in blood pressure (high or low)
- Changes in level of alertness
- Convulsions

Medical monitoring

The medical monitoring for the study will be done by the PI and co-investigators. The PI has overall responsibility for monitoring the integrity of the study data and participant safety. This information, as well as any other unanticipated problems involving risks to subjects or others, will also be reported to the FDA.

Study Procedures

Venipuncture: The risks of drawing blood from a vein include discomfort at the site of puncture, possible bruising and swelling around the puncture site, rarely and infection, and uncommonly faintness from the procedure.

Swallow Study: The radiation exposure from the videofluoroscopy study is thought to be minor. However, the effects of radiation add up over a lifetime. Repeated exposures may increase risk of injury or disease. When deciding to enter this study, we will ask patients to consider previous and future potential exposures. Examples would include x-rays taken for a broken bone or radiation therapy treatments for cancer.

Reporting Timeline for adverse events

- Within **24 hours** (of learning of the event), investigators must report any reportable Serious Adverse Event (SAE) that:
 - Is considered life-threatening/disabling or results in death of subject
- OR-
- Is Unexpected/Unanticipated
- Investigators must report all other reportable SAEs within **5 working days** (of learning of the event).
- All other (suspected) reportable AEs must be reported to the RDCRN within **20 working days** of the notification of the event or of the site becoming aware of the event.

Local institutional reporting requirements to IRB, any GCRC oversight committee and the FDA, if appropriate, remain the responsibility of the treating physician and the Study Chair.

Serious adverse events: The PI and will determine causality (definitely not related, probably not related, possibly related, probably related, definitely related) of the adverse event. This will be reviewed with each event by the D/OSMB. The D/OSMB may request further information if necessary and possibly request changes to the protocol or consent form as a consequence of the adverse event. A back-up notification system is in place so that any delays in review by the D/OSMB beyond a specified period of time are forwarded to a secondary reviewer. The Adverse Event Data Management System (AEDAMS) maintains audit trails and stores data (and data updated) and communication related to any adverse event in the study.

Non-serious expected adverse events: Except those listed above as immediately reportable, non-serious expected adverse events that are reported to or observed by the investigator or a member of his/her research team will be submitted to the D/OSMB in a timely fashion (within 20 working days). The events will be presented in tabular form and given to the D/OSMB on a monthly basis. Local site investigators are also required to fulfill all reporting requirements of their local institutions.

Study Discontinuation

The FDA or IRB have the authority to stop or suspend this trial at any time. This study may be suspended or closed if:

- Early stopping rules have been met (evidence of clear benefit to individuals with PWS before accrual has been met)
- Accrual has been met
- The study objectives have been met
- The Study Chair / Study Investigators believe it is not safe for the study to continue
- The FDA suspends or closes the trial

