Summary of Analytic Approach: The primary outcome measure is change in competency of suck and swallow as determined by videofluoroscopy.

Detailed Description of Analyses

1. Preliminary Analyses:
 - a. Primary Analyses: Analyses for Specific Aim (1): To compare IN-OT vs. placebo with respect to improvement in the competency of suck and swallow.

- b. Early Feeding Skills Assessment- Improvement
 - i. All tests will be two-tailed with an alpha level of 0.05.
 - ii. The relationship between feeding skills improvement and treatment will be assessed using swallowing competency on videofluoroscopy as well as scores on the EFS to evaluate if IN-OT significantly improves feeding, as rated by a clinician, when compared to placebo.
- c. Eye contact, daytime alertness, and parent/infant bonding – Improvement
 - i. Using the Tobii eye tracking device we will assess degree of eye contact of infant
 - ii. Parent/infant bonding will be assessed using the Mother-Infant Bonding Questionnaire (MIBQ) to evaluate if IN-OT significantly improves eye contact and bonding as compared to placebo.
- d. Safety Analyses
 - i. Rates of specific side effects and other adverse events will be tabulated and compared between treatment groups using the chi-square test. Please see the section labeled “Safety Analyses” for further details on how adverse events will be monitored and rated.

Power Analysis: Sample size justification: The target sample size for this Phase 2 trial is 15 patients. The power for the study has been calculated to generate a detectable signal with the sample size of 14 subjects. With this sample size, the study will have 80% power to detect a minimum effect size of $d = 0.8$ standard deviations in the outcome measures between groups using a two-sample T-test and a two sided Type I error rate of 5%. The study is powered based on a conservative estimate from the infant population studied in France.

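### The Outcome Measures section rests project outcomes on an unranked set that omits the one named primary, and the closure list cites benefit-stopping rules that appear nowhere

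*Combined protocol and SAP*

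**What the plan says.** **Named primary.** The Summary of Analytic Approach states: "The primary outcome measure is change in competency of suck and swallow as determined by videofluoroscopy". Item 1.a of the Detailed Description of Analyses carries the same comparison: "Primary Analyses: Analyses for Specific Aim (1): To compare IN-OT vs. placebo with respect to improvement in the competency of suck and swallow". The Objective agrees in substance. The trial is to "compare the change from baseline to day 5 of IN-OT on suck and swallow competency", with the follow-up swallow study on the day after Day 5. The Objective calls this the overall objective; only the analysis section uses the word primary.

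**Outcome Measures.** This section says: "Project outcomes will be determined by changes in eye tracking and in aspiration and penetration on videofluoroscopy swallow study from baseline" to the day after Day 5, and then adds "comparisons of Day 6 measures between active treatment and placebo groups". It does not mention competency and does not rank its measures.

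**Where those measures sit elsewhere.** Eye contact belongs to Study Hypothesis 2 and to item 1.c ("Using the Tobii eye tracking device we will assess degree of eye contact of infant"). The Approach section has a speech pathologist determine competency and lists penetration and aspiration risk as a further assessment bearing on the safety of oral feeding.

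**Error rate.** Item 1.b says "All tests will be two-tailed with an alpha level of 0.05". The Power Analysis claims 80% power with 14 subjects (target 15) for an effect of 0.8 "standard deviations in the outcome measures between groups using a two-sample T-test and a two sided Type I error rate of 5" per cent. No multiplicity rule is given.

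**Benefit stopping.** Study Discontinuation lists, as a ground for closure, that early stopping rules based on clear benefit have been met. No rule, look or boundary is given. Study Oversight has the monitoring board review accrual, adverse events and protocol compliance. Data Management speaks only of a final analysis.

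**The concern.** The section that defines the outcomes leaves out the outcome the analysis section calls primary, and says that other measures will determine the result. A reader following Outcome Measures could present an eye-tracking finding, with no gain in swallowing, as the project's outcome, although the objective and the primary analysis ask about swallowing. For the measures listed there, both a change from baseline and a Day 6 comparison are named, so the choice between them could be made after the data are seen. The Power Analysis does not settle which section governs, because it refers to outcome measures in the plural.

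The benefit-stopping item is a separate matter. It cites rules that do not exist, in a trial whose stated 5% presumes one final test.

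**Working it through.** **1. The plan's own power figure.** Inputs from the Power Analysis: d = 0.8, two-sample t-test, two-sided 5%, 14 subjects (target 15). Allocation is 2:1 (Research Strategy and Feasibility). Noncentrality = d / sqrt(1/n1 + 1/n2).

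| Split | Noncentrality | df | Critical t | Power |
|---|---|---|---|---|
| 9 vs 5 | 1.434 | 12 | 2.179 | 26% |
| 10 vs 5 | 0.8/sqrt(0.1 + 0.2) = 1.461 | 13 | 2.160 | 27% |
| 7 vs 7 | 1.497 | 12 | 2.179 | 28% |

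The stated 80% does not reproduce. A one-sample or paired t-test with n = 14 gives 79%, but that is not the stated test. If 0.8 SD is instead the Day 6 difference, the standardised effect on change is 0.8/sqrt(2(1 - r)), where r is the baseline-Day 6 correlation. That is 0.68, 0.80 or 1.03 for r = 0.3, 0.5 or 0.7, and the power of the change test is 21%, 27% or 42%.

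**2. Named primary governs.** One final test at 0.05 gives an error rate of 5%.

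**3. Outcome Measures list followed, every test at 0.05.** Two measures by two contrasts make four tests. If all were independent: 1 - 0.95^4 = 18.5%. Change and Day 6 for the same measure are correlated, so this was simulated with no treatment effect, 10 versus 5 and pooled t-tests.

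| Assumed r | One measure, change or Day 6 | Two independent measures, four tests |
|---|---|---|
| 0.3 | 8.9% | 17% |
| 0.5 | 9.2% | 17-18% |
| 0.7 | 9.5% | 18% |

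As a check, for independent measures the last column is 1 - (1 - p)^2 with p from the middle column: 1 - 0.908^2 = 17.6% at r = 0.5.

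Three assumptions are not in the documents. Outcome Measures attaches the between-arm wording only to the Day 6 comparison, so a between-arm test of change is assumed. Both measures are taken as continuous, and as independent of each other. Relaxing the last two lowers the rate. With one contrast per measure, the chance of either being significant is 9.8% at zero correlation between measures and 8.5% at 0.7. If aspiration/penetration is yes/no and tested by Fisher's exact test, it is 5.8-7.7%, over assumed event rates of 0.2 to 0.7.

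**4. How often the two contrasts disagree.** With a true Day 6 effect of 0.8 SD and the same r values, exactly one of change and Day 6 is significant in 24%, 28% and 37% of trials. This again assumes that both are compared between arms.

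**5. Benefit look, if taken.** One unadjusted test at 0.05 plus the final test at 15, with no effect and 2:1 allocation at the look, gives 9.0% (look at 6 infants), 8.1% (at 9) or 7.3% (at 12). The look times are assumptions, since the plan schedules none.

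**The case against.** The best reply is that the plan does have one primary. The analysis section names it and the objective matches it. Outcome Measures speaks of project outcomes and never uses the word primary, so an ordinary reading lets the named primary govern. That stands, and the error rate is then 5%. A reader might infer two rival primaries, or a trial running at 17-18%; the documents support neither. They show a clear designation beside an unranked list that has not been reconciled with it.

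A second reply is that aspiration and penetration are part of the swallowing question. Study Hypothesis 1 links better suck and swallow to lower aspiration risk, and the Figure 2 caption pairs the two. This partly stands: the videofluoroscopy half of the list may be a loose statement of the same domain. But the Approach section treats these assessments as additional, and no passage equates them with competency. Eye tracking cannot be explained this way. The contrast is also not open for the primary, which is stated as change; it is open only for the measures in Outcome Measures.

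On stopping, the item may be leftover wording. A reader might infer a planned unadjusted interim look, but the board's listed reviews contain no efficacy data and only a final analysis is mentioned. The 7-9% is therefore conditional on a look that nobody has scheduled.

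**Conclusion.** The concern holds as a conflict of wording that bears on what the efficacy conclusion rests on. Outcome Measures omits the named primary and says an unranked set will determine the project's outcomes. The error rate is 5% if the analysis section governs with one final test. It is about 17-18% over four tests if Outcome Measures is followed with each test at 0.05, under the assumptions in step 3, and lower if the measures are correlated or one of them is yes/no. The benefit-stopping reference is a smaller, separate gap, worth about 7-9% only if one unadjusted look is actually taken. The amendment should be made, since it costs only wording and settles the basis of the conclusion before data are seen.

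**What to change.** (a) Amend Outcome Measures to match the Summary of Analytic Approach: the efficacy conclusion rests on one between-group comparison of change in suck/swallow competency from baseline to Day 6. Label EFS, eye tracking and MIBQ as secondary, with one stated contrast each, reported as estimates with 95% confidence intervals. Treat aspiration/penetration the same way, unless it is expressly made the competency measure before the first infant is randomized.

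(b) Tie the Power Analysis to that one primary only together with restating its figure. At d = 0.8 SD on the analysed scale, 10 versus 5, two-sided 5%, power is about 27%. Changing the outcome wording while leaving 80% in place would attach a wrong figure to the primary.

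(c) Reconcile Study Discontinuation with Study Oversight and Data Management. Either remove the reference to benefit-stopping rules and state that no interim efficacy analysis will be done, or specify the rule with its alpha adjustment. Leave the safety closure items unchanged.

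The cost is wording only: no added infants, visits or assessments. The sponsor gives up a headline claim on the secondary outcomes and, if the reference is removed, an early-benefit stop that the plan never specified.
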